8. RESEARCH METHODS

8.1. Study Design

This is a drug utilization study (DUS) using a non-interventional follow-up (cohort) design with secondary use of data collected from 5 European rheumatology registries (from Denmark, Germany, Spain, Sweden, and the UK). The study fulfills the criteria of a non-interventional PASS.

The study population will include all patients enrolled in the 5 registries with moderate to severe active RA who initiate treatment with filgotinib following approval in Europe,

launch/commercial availability for the treatment of RA and implementation of the aRMMs in each country.

The observational study period in each registry will start with the first patient identified with filgotinib use after launch/commercial availability for the treatment of RA and implementation of the aRMMs in each country and will end 48 months after identification of the first filgotinib patient in each registry.

[figure not shown]

Figure 1 Summary Schematic of the aRMM PASS

The above figure depicts the PASS execution for each registry from which 2 reports will be generated, an interim and a final study report. Therefore, given that the registries will start at differing times, the time to complete the data collection for the overall study will last longer than 48 months. The figure also indicates that a median of 12 months follow-up and 24 months follow-up will be collected at 24 and at 48 months, respectively. This is, however, a maximum estimation as the uptake of filgotinib is unlikely to be uniform, with greater uptake towards the latter part of the study period.

The time required to produce the reports will vary due to data delays associated with the process of data linkage and thus may not be ready at 9 or 12 months, respectively, from the end of the observational periods.

8.2. Setting

8.2.1. ARTIS (Sweden)

Sweden is a Scandinavian country with 9.7 million inhabitants. The prevalence of RA in Sweden is around 0.7% and the overall incidence is around 40/100,000 per year (S. Eriksson et al., 2013; Martin Neovius et al., 2011).

Swedish healthcare is tax-funded and offers universal access. Hospital referral is based on geography rather than insurance status. Patients with RA are typically treated by rheumatologists, the vast majority of whom work in public and hospital-based clinics.

Health and demographic information are collected in a series of registries with a high degree of completeness resulting from the mandatory and semiautomated registration of their data. Based on each Swedish resident's unique personal identification number, issued to all Swedish residents alive in 1947 or born/immigrated thereafter, linkage of data from different registers is possible (Ludvigsson et al., 2009). The registers are maintained by governmental bodies (the main registers used in this project are held by the National Board of Health and Welfare [Socialstyrelsen] and Statistics Sweden [Statistiska centralbyrån]), who may perform data linkages and provide deidentified data for research purposes.

Use of biologic and other targeted RA treatments in Sweden has never been subject to any formal approvals (except for a period during 2002-2003, when manufacturing issues led to reduced availability of etanercept), mandatory treatment histories, or disease activity indices. Instead, the Swedish Society for Rheumatology has issued guidelines for the use of biologics, which are revised on an annual basis, but the ultimate decision to treat with biologics is and has always resided with the treating rheumatologist.

The Swedish Rheumatology Quality Register and ARTIS Registries

[figure not shown]
The Swedish Rheumatology Quality Register (SRQ) was started in 1995 by the Swedish Society of Rheumatology to improve the healthcare and treatment for patients with RA (J. K. Eriksson et al., 2014). SRQ followed on regional register initiatives to enable a national real-world documentation of many different aspects of RA and developed over time into a harmonized national register. SRQ was started mainly for patients with RA, but over time it has been expanded to cover several other rheumatic diseases including ankylosing spondylitis, psoriatic arthritis, myositis, and systemic lupus erythematosus. Initially focusing on early RA, SRQ has gradually come to include also other segments. Currently, SRQ encompasses data on approximately 80% of all patients with RA seen in rheumatology.

Since 1999, ARTIS has been running a safety surveillance database for immunomodulators as part of SRQ, including all presently available and new therapies used for the treatment of patients with inflammatory rheumatic diseases. It covers approximately 90% of all biologic initiations in Sweden after 1999 (M. Neovius et al., 2011; Wadström et al., 2015).

To maintain this high percentage and further improve completeness, the Swedish Society for Rheumatology regularly holds scientific meetings to present surveillance data. The register managers and research nurses regularly visit participating centers to support the clinicians in managing the web-based forms and/or entering information. In each of the 6 geographical regions, at least 1 rheumatologist is assigned as responsible for registration. These rheumatologists are included in the ARTIS steering committee.

- By June 2017, the follow-up within ARTIS included more than 40,000 patients (65% women) and more than 80,000 biologic treatment initiations. Mean age at start of biologic treatment is approximately 50 years. The treatment indication is RA or polyarthritis among

52% of the patients. Figure 2 depicts the accumulated number of patients, and Figure 3 shows the total number of treatment episodes and their distribution across specific drugs.

Dashed line, across all indications; bold lines, RA.

Figure 2 Accumulated Number of First Ever Biologic Initiations Registered in the Swedish Rheumatology Quality Register (SRQ)

[figure not shown]

Figure 3 Cumulative Number of Treatment Initiations in the Swedish Follow-up on Biologics Treatment Among Patients with Rheumatic Diseases

ARTIS is designed to assist in signal detection (through facilitated reporting and contextualization of ADRs), signal evaluation (through register linkage-based evaluations of putative adverse outcomes), and for the short- and long-term evaluation of drug safety and changes in comorbidity patterns via biologic, biosimilar, and targeted therapies (through comparative analyses of risks and determinants for comorbidities and safety outcomes based on linkage data).

8.2.2. BIOBADASER (Spain)

BIOBADASER is a prospective follow-up study assessing the long-term safety of biologic, biosimilar, and other targeted treatments in patients with rheumatic diseases. BIOBADASER was created by the Spanish Society of Rheumatology (Sociedad Española de Reumatología) and the Spanish Agency of Medicines and Medical Devices (Agencia Española del Medicamento y Productos Sanitarios) in 2000 and continued with Phase II in 2006 aiming to collect information on the safety and adverse events (AEs) in patients who had begun biologic treatment (L. Carmona et al., 2005). BIOBADASER helped to establish the relationship between the tumor necrosis factor inhibitor (TNFi) agents and the reactivation of latent TB in patients with rheumatic diseases (Loreto Carmona et al., 2005; Gómez-Reino et al., 2003, 2007). The appearance of biosimilars and targeted synthetic drugs, and the need expressed by regulatory agencies to assess the effectiveness and safety of these agents in daily clinical practice, together with changes in regulation and legislation in pharmacovigilance, determined the launch of the BIOBADASER Phase III in December 2015 (Sanchez-Piedra et al., 2019).

During the first year of Phase III, 35 centers across Spain participated. Starting in the second year, a maximum of 20 centers that met the quality standards (including being amongst the 20 best recruiters, collaborating in the online monitoring of the register, and having less than 25% failures in monitoring) remained in the registry. As of today, there are 28 participating centers meeting the quality standards.

Approximately 40% of patients enrolled in the registry have a diagnosis of RA. Patients eligible for enrolment in BIOBADASER Phase III are:

- Patients with RA diagnosis who start treatment (or are under treatment) with biologic therapy (except infliximab, etanercept, and adalimumab), biosimilar, or targeted synthetic treatment at a participating center
- Patients with any other diagnosis who start treatment (or are under treatment) with biologic, biosimilar, or targeted therapy at a participating center
- Patients who are being treated with biologics or have had treatment suspended, for any reason, provided that no more than 1 year has passed since they last received treatment and that all the necessary data are available for recording (concerning the patient, treatment, and AEs)
- Patients who authorize the prospective collection of data in accordance with the formula indicated on the informed consent form

The objectives for BIOBADASER Phase III are:

- To identify significant AEs occurring during treatment of rheumatic diseases with biologic, biosimilar, and other targeted therapies and estimate their frequency of occurrence
- To identify unexpected AEs
- To identify significant AEs occurring after discontinuation of treatment
- To evaluate, under non-experimental conditions, the elapsed time until discontinuation of biologic, biosimilar, and other targeted therapies in patients suffering from any rheumatic pathology, as well as the reasons for this interruption (secondary effects, ineffectiveness or loss of the biologic effectiveness, remission, or death)
- To evaluate changes in disease activity of patients enrolled in the registry

8.2.3. BSRBR-RA (UK)

BSRBR-RA is a registry-based on an ongoing prospective non-interventional cohort study design that was established in 2001 in the UK. The primary aim of BSRBR-RA is to study the long-term safety of biologic and other targeted therapies in patients with RA. For the first 7-8 years, the main focus was on the study of the safety profile of the first 3 tumor TNFi agents (i.e. adalimumab, etanercept, and infliximab) as a class and as individual therapies. With the exception of the risk of developing TB, BSRBR-RA has not demonstrated any clear differences in AE profiles between these agents. At the time, the most appropriate comparison group for these 3 TNFi agents were patients with active RA receiving treatment with conventional synthetic disease-modifying antirheumatic drugs (csDMARDs).

Several new biologic, biosimilar, and other targeted therapies have since been developed and are receiving National Institute for Health and Clinical Excellence (NICE) approval. Some of these drugs are being used after TNFi therapy and some are proposed for first-line use following csDMARD failure. These agents are all targeted therapies and act on cells, cytokines, or other pathways that play a key role in inflammation and the functioning of the immune system. With each new agent there has to be concern as to what the safety profile may be in routine clinical use. There is an increased risk of premature mortality, serious infection, cardiovascular disease, and lymphoproliferative malignancy in patients with RA and other connective tissue diseases, independent of the treatment they have received. Thus, the patients most likely to receive these new therapies are already at increased risk of adverse outcomes.

The British Society for Rheumatology (BSR) treatment guidelines recommend that all patients receiving biologic, biosimilar, or other new targeted therapies for RA should be registered with the BSRBR-RA. It is recognized though that recruitment may be affected by external factors in the UK such as NICE technology assessment, funding by National Health Services (NHS)/trusts, uptake by prescribing rheumatologists, and local issues at sites including resources. Patients eligible for enrolment in BSRBR-RA include RA patients with a diagnosis of RA by a consultant rheumatologist who are within 6 months of first exposure to a biologic, biosimilar, or other new advanced therapy drug, who have had a minimum of one treatment with a biologic, biosimilar, or other advanced therapy agent, are aged 16 years or older (no upper age limit), and who show willingness to give informed consent for long-term follow-up.

The BSRBR-RA study is being conducted in accordance with legal and regulatory requirements, as well as with scientific purpose and will follow accepted research practices described in the guidelines for Good Pharmacoepidemiology Practices (GPP) for Post-Authorisation Safety Studies, EMA and the European Network of Centres for Pharmacoepidemiology and Pharmacovigilance (ENcEPP) Guide on Methodological Standards in Pharmacoepidemiology.

8.2.4. DANBIO (Denmark)

The DANBIO database is a nationwide Danish registry for research use in rheumatologic diseases such as RA, axial spondyloarthritis, and psoriatic arthritis. It has been approved by the National Board of Health and serves as a clinical database that monitors clinical quality of treatment using selected quality indicators for patients with RA in Denmark (Hetland, 2011).

Initially, DANBIO was a voluntary registry only including patients treated with biologic drugs; but, since 2006, it has been mandatory to also include newly referred RA patients regardless of treatment and disease duration (Ibfelt et al., 2016). By 2015, more than 26,000 patients registered with RA had been included in DANBIO.

Patients are reported to the database at the time of diagnosis, referral to specialized treatment, including biological therapy at the hospital, or in a private rheumatologic clinic. At the first registration, the diagnosis, date of diagnosis, age, sex, and previous medical treatment are registered. Detailed longitudinal clinical information about representative disease course, patient reported outcomes, joint examinations, medical treatment, and side effects of treatment (if any) are collected as part of routine care (Hetland, 2011; Schmidt et al., 2015).

DANBIO is easily linked to other data sources (including the Danish National Patient Register, the Danish Cancer Registry, or administrative registries holding socioeconomic information in Statistic Denmark) using the unique personal identification number assigned to all Danish citizens. A nationwide biobank (i.e. blood and synovial fluid) associated with DANBIO was established in 2015 (Hetland, 2011).

8.2.5. RABBIT (Germany)

The German biologics registry RABBIT is an independent academia driven long-term observational cohort study of patients with RA. RABBIT is being conducted by Deutsches Rheuma Forschungszentrum Berlin (German Rheumatism Research Center [DRFZ]) with joint pharmaceutical industry funding. The aim of the registry is to provide safety and effectiveness data on all licensed biologic and other targeted synthetic therapies provided they are available for the treatment of RA and the respective company is participating in RABBIT. The major aims of the registry are:

- To study the long-term safety of biologic agents and JAK inhibitors. This includes the observation of all AEs and SAEs in order to assess the overall safety profile. Specific emphasis will be put on the “events of interest”
- To describe the long-term effectiveness of treatment with biologic agents and JAK inhibitors (disease outcomes on therapy as well as after terminating therapy). Major outcomes include disease activity (disease activity score 28 [DAS 28] response, clinical disease activity index

[CDAI], simplified disease activity index [SDAI] or DAS 28 remission), American College of Rheumatology (ACR) 20/50/70 response, time under therapy, health-related quality of life and functional status.

- To describe health care consumption and work disability with different drugs.

RA treating physicians who want to participate in RABBIT must sign a contract with the DRFZ. The principal investigators, the scientific advisory board, and the pharmaceutical companies sponsoring the study have no influence on treatment decisions. The type of treatment administered and the conduct of individual therapy including dosages is solely determined by the treating physician in agreement with the patient. Patients registered in RABBIT should have: a diagnosis of RA (up to December 2016: per ACR 1987 criteria; or since January 2017: per diagnosis by a rheumatologist and indication of the number of ACR 1987 criteria met); age of RA onset >15 years; initiated treatment with a licensed biologic agent or JAK inhibitor; initiated treatment with csDMARD (without concomitant biologic or targeted therapy) after failure of at least 1 csDMARD (control group); and provided a signed informed consent.

8.2.6. Index Date, Follow-up, Inclusion and Exclusion Criteria

For all analyses, the index date in each registry will be the date a patient starts filgotinib treatment (i.e. the date of first identification of filgotinib exposure in the registry) on or after launch/commercial availability for the treatment of moderate to severe RA and implementation of the aRMMs in each country. The patient follow-up time is defined as the time from the filgotinib index date until the earliest of treatment discontinuation, study withdrawal (withdrawn from the registry, death or loss to follow-up) or end of study.

The observational (study) period for each registry starts at the index date of the first patient starting filgotinib treatment in the registry (i.e. start of data collection). End of the study period will be at 48 months after the start of data collection in the registry (i.e. end of data collection).

To be included a patient has to be aged 18 years or older at the index date. Further inclusion criteria are specified in the following sections for each registry; patients must meet all eligibility criteria.

There are no restrictions to patient inclusion in terms of either historical data or minimum amount of follow-up. Furthermore, patients can be included if they have previously used filgotinib, in which case the patient will have 2 or more treatment lines and therefore 2 or more index dates.

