8.2.7. Inclusion Criteria

All patients initiating filgotinib in the observational period to treat moderate to severe RA and who comply with the register's requirements for inclusion (including patient consent) will be included. Thus, there is no limit in terms of age, although only adults (≥ 18) are included in ARTIS, or in terms of prior use of filgotinib; initiation is therefore defined as either no prior use or prior use that was discontinued (thus, patients who are non-naïve to filgotinib can be included).

1. Initiation of filgotinib treatment in the observational periods as captured in ARTIS.

2. RA diagnosis by a consulting rheumatologist.

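### BIOBADASER and BSRBR-RA can enrol patients after filgotinib has started, but Section 8.2.6 has no rule for late entry and Section 8.9 claims complete capture

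*Protocol*

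**What the plan says.** Section 8.2.6 defines the index date as "the date a patient starts filgotinib treatment (i.e. the date of first identification of filgotinib exposure in the registry"), on or after launch and implementation of the risk minimisation measures. Follow-up then runs as follows: "The patient follow-up time is defined as the time from the filgotinib index date until the earliest of treatment discontinuation", study withdrawal (which includes death) or end of study. The section adds: "There are no restrictions to patient inclusion in terms of either historical data or minimum amount of follow-up". Nothing is said about entry after the index date.

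Section 8.2.7 makes the registries' own entry rules part of eligibility: patients who meet each register's "requirements for inclusion (including patient consent) will be included". Those rules differ:

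- **BIOBADASER (8.2.2)** lists "Patients with RA diagnosis who start treatment (or are under treatment) with biologic therapy", with targeted synthetic drugs named later in the same criterion. No maximum time since start is given. A further criterion admits patients on biologics, or whose treatment was suspended, "provided that no more than 1 year has passed since they last received treatment" and that the necessary data can be recorded.
- **BSRBR-RA (8.2.3)** takes patients "who are within 6 months of first exposure to a biologic, biosimilar, or other new advanced therapy drug" who have had at least one treatment. It does not ask that the patient still be on the drug.

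Sections 9.3.2 and 9.3.3 confirm that participants in both registries have given informed consent.

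Section 8.9 raises selection bias and sets it aside on the ground that the study captures every initiator.

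**The concern.** A registry that accepts patients some time after treatment start sees only those who were still available to be enrolled. Section 8.2.6 handles them as if they had been observed from the first dose. Two things follow.

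First, the set of initiators is filtered by what happened between start and enrolment. Anyone who died in that interval is missing. Anyone who stopped early may be harder to recruit.

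Second, for a late entrant the interval from start to enrolment is free of death by construction, yet it counts as follow-up if the index date is read as the treatment start.

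The study exists to measure uncommon adherence failures: starts in contraindicated patients, pregnancy or TB on treatment, and continuation after VTE. These may be linked to early stopping, so a filter that depends on early course could move the proportions being reported. Section 8.9 gives the reader no warning. The ENCePP checklist in Annex 2 cites Section 8.9 for information bias, a heading whose examples include time-related bias, but Section 8.9 does not discuss entry timing.

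**Working it through.** **1. Who can be missed, by rule.**

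| Patient before enrolment | BIOBADASER | BSRBR-RA |
|---|---|---|
| Still on filgotinib | Can enter; no stated maximum time since start | Can enter within 6 months of first exposure |
| Stopped filgotinib | Unclear: the 1-year criterion is worded for biologics, and filgotinib is a targeted synthetic drug | Can enter within the window; one treatment is enough |
| Died | Cannot consent, cannot enter | Cannot consent, cannot enter |
| Already registered, then starts filgotinib | No late entry | No late entry |

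Only death before consent is a certain loss. Loss of stoppers is possible in practice but is not fixed by the criteria.

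**2. The two wordings of the index date.** For a late entrant, treatment start and first identification in the registry are different days. On the first reading, the pre-enrolment interval enters follow-up. On the second it does not, but the baseline then describes a patient already on treatment. The filter on who enters is the same on both readings.

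**3. The plan's own figure.** Table 10 uses the rule of three, n = 3/p. At p = 1%, 3/0.01 = 300. The exact value is ln(0.05)/ln(0.99), rounded up to 299. With n = 300 the chance of at least one case is 1 − 0.99^300 = 95.1%. The table is correct for an unselected sample.

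**4. Sensitivity to selective loss.** Let p be the true proportion, L1 the share of contraindicated starters lost before enrolment, and L0 the share of other starters lost. Then

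observed = p(1 − L1) / [p(1 − L1) + (1 − p)(1 − L0)].

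Example with p = 1%, L1 = 20%, L0 = 5%: 0.0080 / (0.0080 + 0.99 × 0.95) = 0.0080 / 0.9485 = 0.84%. The chance of at least one case among 300 enrolled is 1 − (1 − observed)^300.

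| L1 / L0 (assumed) | Observed, true 1% | At least one case in 300 |
|---|---|---|
| 5% / 5% | 1.00% | 95.1% |
| 10% / 5% | 0.95% | 94.3% |
| 20% / 5% | 0.84% | 92.1% |
| 30% / 10% | 0.78% | 90.4% |
| 50% / 10% | 0.56% | 81.3% |
| 5% / 20% | 1.19% | 97.2% |

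The losses are assumptions; the protocol gives none. The table also treats all 300 patients as coming from an affected registry, so the effect on a five-registry total would be smaller.

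**5. How large could loss from stopping be?** Assume 10% to 40% of starters stop per year at a constant hazard. The share stopped by month 6 is 1 − (1 − a)^0.5, which gives 5.1% at a = 10% and 22.5% at a = 40%. These are ceilings: they are reached only if every patient enrols at month 6 and no stopper can enrol, which the criteria do not say.

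**6. Discontinuation after VTE.** Let d be the true share who stop after a VTE and L the share of those stoppers lost before enrolment, with no loss among those who continue. The observed share is d(1 − L) / [d(1 − L) + (1 − d)], which is below d whenever L > 0 and 0 < d < 1. Here the loss makes adherence look worse.

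**The case against.** Several objections are fair.

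- **Late entry is not unlimited in both registries.** A reader might infer that neither sets a limit. BSRBR-RA has a 6-month window; only the BIOBADASER criterion for patients under treatment has no stated maximum.
- **Stoppers are not shut out.** A reader might infer that anyone who stopped before enrolment can never enter. BSRBR-RA needs one treatment only. BIOBADASER's 1-year criterion may admit stoppers, though its wording for biologics leaves its reach to filgotinib open.
- **The direction is not established.** It is tempting to conclude that contraindicated or harmful use is understated. That needs heavier loss among those patients, which nothing in the protocol shows. Equal loss gives no bias, reverse loss overstates, and the VTE objective moves the other way.
- **A contrast with RABBIT is not supported.** Section 8.2.5 also requires initiated treatment and signed consent, and states no maximum interval.
- **Immortal time has little to act on.** Section 8.7 plans numbers and proportions of patients, not rates. Section 8.3.2 mentions exposure time but specifies no person-time rate. For the baseline proportions the issue is selection.
- **Entry timing could be left to the SAP.** Detailed methods may be. But the start of follow-up is fixed in 8.2.6 and the completeness claim is made in 8.9, and both are protocol text.

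These points limit the size and direction that can be claimed. They do not remove the missing late-entry rule, the certain loss of deaths before consent, or the conflict with Section 8.9.

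**Conclusion.** The point holds in a limited form. Two of the five registries can enrol consenting patients after filgotinib has started. Section 8.2.6 treats them all as initiators followed from start, with no provision for late entry. Deaths before consent are lost, and early stoppers may be under-represented. The at-initiation and on-treatment proportions from BIOBADASER and BSRBR-RA may therefore be selected, and the claim of complete capture in Section 8.9 does not follow from the entry criteria.

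No single corrected figure can be given, because the protocol states no enrolment lag, early stopping rate or early death rate. The 0.56% to 1.19% range for a true 1% rests entirely on the assumed losses and shows sensitivity, not an estimate. Patients already registered when they start filgotinib are unaffected, so the share enrolled late sets the scale of the problem. The study should report that share.

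**What to change.** 1. In Section 8.2.6, define the filgotinib start date and the registry enrolment date as two separate dates, and say which one is the index date.
2. Report, per registry, the distribution of the lag from start to enrolment and the share of treatment lines enrolled late.
3. Present the at-initiation and on-treatment proportions separately, or as a sensitivity analysis, for treatment lines where the patient was enrolled before or close to filgotinib start and for later entrants. A cut-off such as 30 days is a convention; the registries should settle it before the data are analysed.
4. If any person-time rate is calculated, count both events and time at risk from the later of the two dates. Do not carry this rule over to the simple proportions: dropping pre-enrolment events from the numerator while keeping those patients in the denominator would itself understate the proportion.
5. Qualify Section 8.9: capture depends on enrolment and consent, starters who died before consent are missed, and early stoppers may be.

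The cost is one derived variable and a few sentences. The enrolment date is not among the baseline variables listed in Sections 8.3.1.2 and 8.3.1.3, so it must be added to the data request. The downside is smaller numbers, and wider intervals, in the early-enrolled stratum.
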